9.7.4.2. Quantitative bias analysis for unmeasured confounding

A quantitative bias analysis will be conducted to assess the potential magnitude of bias due to unmeasured confounding, including confounding by incompletely captured or missing covariates (eg, risk factors for progression to severe COVID-19 such as smoking or obesity). These analyses use informed estimates from the literature to identify the strength of unmeasured confounding that would be necessary to explain observed associations between the treatment (cohort membership) and outcomes (Schneeweiss 2006).

9.7.4.3. Quantitative bias analysis for unobserved outcomes

Because exposed pregnancies may be accrued (via observed Z3A codes) but which have no observed pregnancy outcome, and because completed pregnancies may not link to infants in the insurance databases, characteristics of pregnancies with and without observed outcomes, as well as livebirth pregnancies with and without linkage to infant(s) will be described according to baseline covariates. If substantial differences are observed, a sensitivity analysis will be performed in which comparative analyses are weighted to adjust for censoring due to missing pregnancy outcomes or non-linkage.

9.7.4.4. Comparator-specific analyses

Due to the differing mechanisms of action, routes of administration, and contraindications between comparator medications included in Cohort 2, an analysis will be performed in which, sample size permitting, each comparator drug is compared to PAXLOVID individually.

9.7.4.5. Any PAXLOVID exposure analysis

Because restricting the PAXLOVID cohort (Cohort 1) may select for patients with fewer risk factors for progression to severe COVID-19 by excluding patients requiring subsequent therapies after failure of PAXLOVID (ie, healthier patients), a sensitivity analysis will redefine the PAXLOVID cohort to include all pregnancies with any exposure to PAXLOVID during an exposure window, regardless of other therapies. This cohort will be compared, via IPTW, to the cohort of pregnancies exposed to other therapies but without exposure to PAXLOVID (Cohort 2).

9.7.4.6. Log-binomial analyses

Calculation of prevalence ratios will be conducted using log-binomial analyses instead of Poisson regression, following the approach described in section 9.7.2.

9.7.4.7. Subgroup analyses

Some women may be at a higher risk for certain pregnancy or infant outcomes. The balance of such high-risk attributes will be compared across cohorts, and an analysis will be performed that generates sub-group-specific estimates by the presence of these attributes. Additionally, descriptive and comparative analyses will be performed for different levels of the following baseline covariates: calendar time of first COVID-19 treatment initiation or infection, as well as by the duration between time of first COVID-19 treatment initiation or infection and ECD.

Additional sub-group analysis by risk factors for adverse pregnancy or infant outcomes observed during pregnancy (eg, infection during pregnancy, hospitalization during pregnancy) may be performed, with the acknowledgement that these may be post-treatment characteristics and thus susceptible to bias if they are affected by treatment. Sub-group specific estimates will be estimated from the Poisson regression model via inclusion of an indicator variable for the subgroup of interest, as well as an interaction term with the treatment indicator.

9.8. Quality control

The ORD contains data derived from claims submitted by providers and pharmacies to obtain payment for health care services rendered, data to track plan membership for premium billing, and provider data to track participating physicians who have contracts with health plans to provide services. The underlying administrative data are routinely captured, verified, automated, and de-identified. The data undergo regular audits and quality control procedures by the insurer and are updated monthly. Although the health insurance claims data represent financial transactions and are not research records, the financial transactions related to the services provided create financial incentives to record them correctly and fully, so the billable medical services represented in the database are likely to be complete.

The conduct and reporting of this study follows Optum Epidemiology's Standard Operating Procedures (SOPs) that are consistent with the ISPE Guidelines for Good Pharmacoepidemiology Practices (GPP) (ISPE 2015) as well as the FDA's Best Practices for Conducting and Reporting Pharmacoepidemiologic Safety Studies Using Electronic Healthcare Data (https://www.fda.gov/regulatory-information/search-fda-guidance-documents/best-practices-conducting-and-reporting-pharmacoepidemiologic-safety-studies-using-electronic) and FDA's Real-World Data: Assessing Electronic Health Records and Medical Claims Data To Support Regulatory Decision-Making for Drug and Biological Products, Draft Guidance, September 2021 (https://www.fda.gov/regulatory-information/search-fda-guidance-documents/real-world-data-assessing-electronic-health-records-and-medical-claims-data-support-regulatory). For pregnancy safety studies such as this, the suggested study design and methodology are consistent with the FDA draft guidance document Postapproval Pregnancy Safety Studies Guidance for Industry

(https://www.fda.gov/regulatory-information/search-fda-guidance-documents/postapproval-pregnancy-safety-studies-guidance-industry). In particular, the SOPs in place at Optum prescribe that processes and deliverables are documented, reviewed, and validated in sufficient detail to allow for subsequent re-examination or replication.

The validation of analytic work typically involves a combination of a review of program logs and lists, independent coding, a review of program processes and documentation to ensure Optum SOPs are followed, and reconciliation of program code with the study protocol to ensure populations and results are consistent with what is needed for the study. Individual programs are documented and revised as needed until sign-off by a validation analyst using the validation/programming log.

9.9. Limitations of the research methods

This study is based on an analysis of automated and prospectively collected medical and prescription claims, supplemented by information abstracted from medical records. While claims data are extremely valuable for the efficient and effective examination of health-related outcomes and effects of different exposures to treatment on those outcomes, all claims databases have certain inherent limitations because the claims are collected for the purpose of payment, not research. Presence of a claim for a filled prescription does not indicate that the medication was consumed or that it was taken as prescribed. Similarly, absence of a claim for a filled prescription does not preclude the possibility of exposure to a medication. Medications filled over-the-counter, provided as samples by the physician, or received during an inpatient hospital stay will often not be observed in the claims data. Presence of a diagnosis code on a medical claim is not positive presence of disease, as the diagnosis code may be incorrectly coded or included as rule-out criteria rather than actual disease. Therefore, a medical record review will be conducted for select outcomes to confirm outcome events that are initially identified in medical claims.

COVID-19 infection will be assessed through the presence of a single diagnosis code, which was shown to have a high but decreasing PPV throughout calendar year 2020 (Kluberg et al. 2022), in a sample of hospitalized patients with known COVID-19 laboratory results covered by a national insurer. The literature regarding accuracy of ICD-10 COVID-19 diagnosis codes will be reassessed throughout the course of the study, and the algorithm for identification of COVID-19 may be modified if superior algorithms are published. If additional treatments with non-COVID-19 indications are included in study cohorts in the future, requiring a COVID-19 diagnosis prior to treatment may be considered for study eligibility.

Additionally, neither information on COVID-19 severity nor reasons for the test that determine the COVID-19 diagnosis are directly available in administrative claims data. Proxy measures for COVID-19 severity (eg, critical care services) have been added to the list of covariates (Section 9.3.3). Options for other proxies of severity and reason for diagnosis will continue to be explored; for example, co-occurrence of diagnoses on days with select other procedures (eg, diagnoses occurring on days with procedure codes for standard prenatal visits) or site of diagnosis may serve as proxies for the reason of diagnosis.

Using ICD-10 Z3A codes to estimate the LMP date (and, subsequently, ECD) is expected to be accurate but, when Z3A codes are not present, using existing algorithms to estimate LMP (that are based on the presence of pregnancy outcomes) is expected to introduce a greater degree of measurement error for early pregnancy outcomes such as SA and induced termination. In addition, given the inexact estimation of LMP, classification of trimesters and the corresponding medication exposure could be inaccurate, with such non-differential misclassification of a binary exposure likely biasing study results toward the null.

In this study, the numbers of some pregnancy and infant outcomes are expected to be low. As the number of variables for inclusion in regression models is dependent on the number of study outcomes, the standard approach to controlling for confounding through regression modelling of the outcomes will yield estimates that are only adjusted for a small number of potential confounders. In contrast, propensity score modelling and IPTW allows for the inclusion of dozens of potential confounders and risk factors, resulting in greater validity of the estimates than what may be derived from regression modelling alone. While it is true that operationally, the IPTW analysis controls for variables that are included in the model and may not fully control for bias due to unknown confounders, it has been shown that, similar to randomization within clinical trials, propensity score modelling and adjustment often controls for confounding due to variables that are not explicitly included in the propensity score model through the inclusion of variables that are proxies for the non-included variables (Guertin et al. 2016).

Residual confounding is a concern due to the difficulty in defining appropriate comparator cohorts. While untreated (or inactive) comparator groups have known issues that limit exchangeability (eg, milder disease), the Untreated Comparator cohorts (Cohort 3) add value by providing an estimate of the background rate of the pregnancy and infant outcomes among diagnosed COVID-19 positive pregnant women. Moreover, though this study will account for a host of pre-pregnancy characteristics, the choice of PAXLOVID versus other COVID-19 therapies may be related to infection severity or other risk factors for progression to severe COVID-19, which could further be related to risk of pregnancy or infant outcomes. The potential magnitude of this bias will be assessed through a quantitative bias analysis which assesses the potential for unmeasured confounding to bias results, including by risk factors for COVID-19 severity.

As PAXLOVID may be the first-line therapy of choice for high-risk COVID-19 patients, restricting Cohort 1 to individuals not receiving other study cohort medications may select for patients with fewer risk factors for progression to severe COVID-19 (ie, healthier patients). This will be assessed by characterizing the number of different treatment types (eg, PAXLOVID followed by remdesivir) received both within and across COVID-19 episodes (if applicable) during a pregnancy, as well as in a sensitivity analysis in which pregnancies with any exposure to PAXLOVID, regardless of receipt of other treatments, are compared to Cohorts 2 and 3.

Identification of infant MCM within this study is limited to pregnancies that result in livebirths that are linked to the infants' data. Therefore, infant MCMs that result in SA,

induced termination, or stillbirth will not be included in the main analysis. Further, infant MCMs that may be noted in the mothers' claims at delivery (whose infants' data are not linked) may be missed. Finally, some infants will have less than a year of follow-up after birth (eg, due to disenrollment or deliveries at the end of the study period). As some MCMs can be diagnosed months after delivery this may result in the incomplete capture of some outcomes but is not expected to bias results (Wacholder et al. 1995). Sensitivity analyses will be conducted to quantify and to describe the potential infant MCMs among pregnancies that resulted in SA, induced termination, or stillbirth and those that may be missed due to nonlinkage of the infant data or infant disenrollment from the health plan.

The study power will be limited until several years of cohort accrual have passed. Because accrual of PAXLOVID-exposed pregnancies depends on actual use within the insured population that is the source for the study, divergence in numbers of users from sample size projections might affect how rapidly the study power reaches an adequate level.

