9.2.3. Identification of pregnancy and estimation of LMP and ECD

Pregnancies will be identified using the Optum Dynamic Assessment of Pregnancies and Infants (DAPI) (Section 9.4.2). This process applies a set of algorithms comprised of International Classification of Diseases, 10th revision (ICD-10) diagnosis and procedure codes, Current Procedural Terminology¹ (CPT) codes, and HCPCS codes to the claims data to identify pregnancies, LMP date, pregnancy end date, and pregnancy outcome (Bertoia et al. 2022).

DAPI uses ICD-10 Z3A codes denoting weeks of gestation to estimate the LMP (Chomistek et al. 2021, Chomistek et al. 2022). The LMP date is the first day of the last menstrual period before pregnancy. Validation of Z3A-based LMP estimation has indicated good performance, with a median difference in days between LMP date based on Z3A codes and adjudicated (via medical record review) LMP date of 4.0 days (interquartile range: 2.0 – 10.0 days). Gestational age is anchored by the LMP date, where 12 weeks gestation is 12 completed weeks after LMP, 30 weeks gestation is 30 completed weeks after LMP, etc. Conception typically occurs about 2 weeks after the LMP date, around ovulation which is midway through the menstrual cycle. ECD will be calculated based on the estimated LMP (LMP + 14 days).

There is a small fraction of pregnancies that do not have Z3A codes; in these cases, DAPI assigns an average length of gestation for different pregnancy outcomes and uses that average length to estimate the accompanying ECD (eg, 39 weeks for full-term births and 10 weeks for all abortions), as described by Hornbrook et al. (Hornbrook et al. 2007). DAPI may be refined over the course of the project based on clinical input and review of published literature.

¹ CPT copyright 2022 American Medical Association (AMA). All rights reserved.

Fee schedules, relative value units, conversion factors and/or related components are not assigned by the AMA, are not part of CPT, and the AMA is not recommending their use. The AMA does not directly or indirectly practice medicine or dispense medical services. The AMA assumes no liability for data contained or not contained herein.

CPT is a registered trademark of the American Medical Association.

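### Section 9.9 calls pregnancy-dating error non-differential and null-biasing, but undated losses are dated from their own outcome, so for spontaneous abortion and induced termination the error is differential and can bias either way

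*Protocol*

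**What the plan says.** Protocol section 9.2.3 estimates LMP from Z3A gestation-week codes and sets ECD at LMP + 14 days. It then adds: "There is a small fraction of pregnancies that do not have Z3A codes". For these, "DAPI assigns an average length of gestation for different pregnancy outcomes", with the example "39 weeks for full-term births and 10 weeks for all abortions".

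Section 9.9 returns to this fallback. It describes the algorithms as ones "that are based on the presence of pregnancy outcomes" and says their use "is expected to introduce a greater degree of measurement error for early pregnancy outcomes such as SA and induced termination". The next sentence turns to trimester and medication-exposure classification under inexact LMP dating and concludes with "such non-differential misclassification of a binary exposure likely biasing study results toward the null". That conclusion is not restricted by outcome or by dating method.

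Exposure is counted from a drug-specific number of days before ECD: 7 for PAXLOVID, 9 for remdesivir and 60 for bebtelovimab (sections 9.2.6.1 and 9.2.6.2). The Cohort 3 diagnosis window also starts 7 days before ECD (section 9.2.6.3). Pregnancy outcomes are described and compared by exposure window, including the first trimester (sections 9.7.2 and 9.7.2.3).

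**The concern.** The two consecutive statements in section 9.9 do not fit together. If the dating rule is chosen by the outcome, and the error is expected to be larger for one set of outcomes, then the exposure error differs by outcome. That is what differential misclassification means, and the usual argument for bias toward the null does not apply to it.

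The practical stake is interpretation. SA is the easiest comparison to power: section 9.5 asks for 127 exposed pregnancies at RR 2.0. It relies on a claims algorithm (section 9.3.1.3) and is not among the outcomes listed for adjudication in section 9.3.1, so no chart-based dating of SA is planned. If the final report carries the null-bias sentence forward, a raised SA or termination ratio would be read as conservative and a null ratio as merely diluted. Neither reading is justified. The absolute first-trimester risks called for by secondary objective 1 are also exposed to this error, even where it cancels in a ratio.

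**Working it through.** The plan gives no figure for this bias, so there is none to reproduce. The check has three parts.

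**1. What the dating rule does to the exposure window.** Inputs from the protocol: assigned length 10 weeks, ECD = LMP + 14 days, pre-ECD windows of 7, 9 and 60 days. For a loss truly at week w (up to the end of the first trimester):

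- true window = pre-ECD days + 7 × (w − 2)
- assigned window = pre-ECD days + 7 × (10 − 2) = pre-ECD days + 56

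| True week of loss | PAXLOVID | Remdesivir | Bebtelovimab |
|---|---|---|---|
| 6 | 63/35 = 1.80 | 65/37 = 1.76 | 116/88 = 1.32 |
| 8 | 63/49 = 1.29 | 65/51 = 1.27 | 116/102 = 1.14 |
| 12 | 63/77 = 0.82 | 65/79 = 0.82 | 116/130 = 0.89 |

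A loss before week 10 gets an ECD that is too early, so pre-conception dispensings count as exposure. A loss after week 10 gets an ECD that is too late, so early exposures fall out. For a loss at week 16, pregnancy ends on day 98 after true ECD and the assigned PAXLOVID window runs from day 35 to day 98. If the first trimester ends at 14 completed weeks (day 84; my assumption), days −7 to 35 are missed and days 84 to 98 are wrongly counted as first trimester.

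**2. Whether the error differs by outcome.** Assumptions: uniform timing of treatment from 60 days before true ECD to pregnancy end; true gestation at loss normal with SD 3 weeks, clipped to about 5 to 20 weeks; term births centred on 39 weeks with SD 1 to 1.5 weeks. First-trimester exposure classification is then:

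| Undated pregnancies | Sensitivity | Specificity |
|---|---|---|
| Losses, mean week 8 | 0.95 | 0.67 |
| Losses, mean week 10 | 0.89 | 0.81 |
| Losses, mean week 12 | 0.79 | 0.88 |
| Term livebirths | 0.91 to 0.94 | 0.97 to 0.98 |

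Specificity differs clearly between losses and livebirths, so the error is differential.

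**3. What this does to SA estimates when PAXLOVID has no effect.** SA is 14% (section 9.5) and gestation at loss is as in part 2. The diagnosis rate in Cohort 3 is constant, and the PAXLOVID dispensing rate changes by a factor q at day 21 after ECD (taken as pregnancy recognition). Each entry is the factor by which the Cohort 1 v Cohort 3 SA ratio is multiplied.

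| Mean week of loss | q | 5% of losses undated | 20% | 50% | 100% |
|---|---|---|---|---|---|
| any | 1 (same timing) | 1.00 | 1.00 | 1.00 | 1.00 |
| 7.5 to 8 | 0.33 | 1.004–1.005 | 1.02 | 1.04 | 1.07 |
| 7.5 to 8 | 2 | 1.00 | 0.98–0.99 | 0.97 | 0.94–0.95 |
| 10 | 0.33 | 1.00 | 1.00 | 1.00 | 1.00 |
| 12 | 0.33 | 1.00 | 0.98 | 0.95 | 0.89 |

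Absolute risk moves more than the ratio. With mean loss at week 8 and q = 0.33, first-trimester SA prevalence in Cohort 1 goes from about 10.5% to 11.2% with 20% of losses undated, and to just under 14% with all undated. Cohort 3 rises as well, which is why the ratio moves less.

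For Cohort 2 the pre-ECD windows also differ. Take undated share m and window ratio k from the first table. The count of exposed losses is multiplied by M = 1 + m(k − 1), and the risk becomes 0.14M / (0.86 + 0.14M). With m = 0.30 and loss at week 6:

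- PAXLOVID: M = 1.24, risk = 0.1736/1.0336 = 16.8%, or ×1.20
- bebtelovimab: M = 1.095, risk ×1.08, crude null ratio 1.20/1.08 = 1.11
- remdesivir: M = 1.227, risk ×1.19, crude null ratio about 1.01

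With m = 0.10 and loss at week 8 the bebtelovimab ratio is about 1.01. At week 12 with m = 0.30 it reverses to 0.98.

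**The case against.** The strongest reply is that this is a hedged sentence in a limitations section. It covers dating error in general, most of which is the small Z3A error (median 4.0 days, IQR 2.0 to 10.0, section 9.2.3), and greater error for early losses is disclosed just before it. That is fair as to tone. It does not rescue the inference, because the conclusion is not limited to Z3A-dated pregnancies.

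Second, the undated group is described as a small fraction. If that also holds among losses, the bias is small (about 0.5% on the ratio against Cohort 3 at 5% undated). This stands as a limit on size. But the stated fraction refers to all pregnancies, and nothing is said about losses.

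Third, the same dating rule applies to every cohort, and the time from index date to ECD is a candidate propensity-score covariate (section 9.3.3.2.1) and a subgroup variable (section 9.7.4.7). If it is modelled, bebtelovimab pregnancies indexed long before ECD would get little ATT weight, removing much of the asymmetry between windows. This largely stands for the weighted comparison with Cohort 2. It does not help the crude ratios or the absolute risks, and for undated losses this covariate is itself computed from the outcome-based ECD.

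Fourth, section 9.1 suggests that full pregnancy may be the more relevant window for pregnancy outcomes, where shifts across the trimester boundary do not matter. That removes part of the mechanism. The miscounting of exposure around conception remains.

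Two stronger readings are tempting. A reader might infer that the rule creates a spurious SA excess. The documents do not support that: the sign depends on when undated losses truly occur and on treatment timing, and 10 weeks is presented as an average. A reader might also multiply case counts alone and arrive at a 24% inflation and a ratio of 1.13 against bebtelovimab. That leaves the added losses out of the denominator, puts every undated loss at week 6, and ignores remdesivir, which is also in Cohort 2.

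**Conclusion.** The point holds for SA and induced termination. By the protocol's own description, dating error for pregnancies without Z3A codes depends on the outcome, so calling the resulting exposure misclassification non-differential and likely toward the null is unsupported for those outcomes.

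Absolute first-trimester risks can be biased in each cohort. Cohort ratios can be biased up or down when treatment timing or pre-ECD windows differ, and are unbiased against Cohort 3 when timing is alike. Under the assumptions above, the factor against Cohort 3 lies within about 0.98 to 1.02 at 20% of losses undated and 0.89 to 1.07 at the extreme of all undated. These ranges rest on assumed loss timing, treatment timing and undated share, none of which the protocol gives; if the undated share of losses is small, so is the bias.

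MCM in linked livebirths is little affected, since the 10-week rule applies only to abortions. The exposure-misclassification analysis in section 9.7.4.1 commits to alternative trimester windows for MCM. The further windows it allows still use the same ECD. Sections 9.7.4.3 and 9.7.4.7 do not vary the dating rule either, so no planned analysis would reveal the problem.

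**What to change.** 1. In section 9.9, limit the non-differential, toward-the-null statement to Z3A-dated pregnancies and livebirths. State that for SA and induced termination the bias may go either way.
2. Report the share of pregnancies without Z3A codes by outcome and cohort. This alone shows whether the issue matters.
3. Add to section 9.7.4.1 a sensitivity analysis of SA and induced termination that re-dates undated losses over a range or distribution of gestational ages (for example, the distribution seen in Z3A-dated losses), re-derives ECD and cohort assignment, and repeats the estimates. Present it alongside an analysis restricted to Z3A-dated pregnancies.

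The cost is modest: two re-runs and some text. The Z3A-only analysis should not stand alone. If undated pregnancies are concentrated among losses, it drops losses preferentially and its absolute risks are biased low, so it should be read mainly for the ratios. The re-dating analysis keeps all losses and is the one to use for absolute risks.
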